## **Research Synopsis**

**Study Population:** This research study will examine the impact of two existing approaches for delivering care within a specialty medical home (SMH) clinical model for patients with inflammatory bowel disease (IBD) and behavioral health (BH) conditions. Care approaches available to patients include traditional high-touch care delivered by a multidisciplinary team of IBD and BH clinicians (TEAM) and a health technology-based (TECH) approach that uses telemedicine and other evidence-based digital tools designed to deliver accessible, convenient care. This study seeks to understand the differential impact of TEAM and TECH on important health outcomes such as IBD and BH symptom severity, functional impairment, health care service utilization and costs, patient quality of life, and patient disease self-management.

**Study Design:** A comparative effectiveness study using an individual-level randomized design along with a pragmatic, mixed-methods approach to compare two evidence -based SMH care strategies (e.g. high-touch multidisciplinary care and low-human touch technology-enhanced care). Quantitative (e.g. self-report, electronic health record, process) and qualitative (e.g. interviews) data will be collected across multiple time points during the study period.

**Sample Size:** We expect to enroll 675 individuals.

**Study Duration:** The contract period begins February 1, 2019 and concludes September 30, 2026. Participants were actively enrolled in the study between July 1, 2019 and February 28, 2024.

**Primary Aim 1:** Examine the impact of TEAM vs. TECH on two main patient-centered outcomes of IBD and BH symptom severity and secondary outcomes of functional impairment, healthcare utilization, quality of life, and self-efficacy.

**Hypothesis 1:** Both TEAM and TECH approaches will result in clinically meaningful improvement across all outcomes.

**Primary Aim 2:** Examine the impact of patient characteristics on clinical response to TEAM or TECH approaches and establish subgroups of patients who will benefit most from each approach. The study focused on baseline IBD activity and age as primary moderators but secondarily explored site, IBD diagnosis, and health literacy.

**Hypothesis 2a:** The TEAM approach will show greater effects in those with active IBD, while TECH will show greater effects in those with inactive IBD.

**Hypothesis 2b:** The TECH approach will improve outcomes more in younger patients.

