## **Background and Significance**

Inflammatory bowel diseases, including Crohn's disease (CD) and ulcerative colitis (UC), are among the most costly gastrointestinal (GI) conditions in the United States (US) and are lifelong chronic diseases that, if not well managed, can significantly disrupt the lives of individuals. IBD afflicts three million U.S. patients and families with incidence rising globally, especially among younger age groups, during a critical social and career development period. IBD is a relapsing and remitting condition associated with varying degrees of GI inflammation (disease activity) and related symptoms of abdominal pain, diarrhea, nutritional deficits and fatigue. In the presence of anxiety and depression, IBD symptom load is even higher, even when inflammation is mild or absent. IBD carries a financial burden between \$14-31 billion annually in the U.S., with about 30% of adult IBD patients accounting for more than 80% of IBD-related healthcare spend; the largest drivers of cost are surgeries and hospitalizations, many of which are preventable. Prior studies have shown that medical utilization (both emergency department (ED) visits and unplanned hospitalizations) is driven by serious disease and IBD activity requiring steroids, biologics, or surgery, chronic unexplained pain and related opioid use, and unaddressed or undertreated behavioral health (BH) problems.

IBD patients exhibit higher rates of comorbid BH conditions, especially anxiety and depression, than healthy counterparts – these further compound disease complexity. Indeed, when present, BH issues directly and negatively impact medical/surgical treatment response, adherence to treatment regimens, care utilization including surgeries, and disease-related quality of life and functioning. Emerging adults with IBD are a large and uniquely vulnerable subpopulation who, if not effectively integrated into an adult-centered healthcare system, are at significantly higher risk for poor disease outcomes, Including high rates of anxiety and depression. Beginning in 2020, BH symptoms were further exacerbated by the COVID-19 pandemic, particularly for IBD patients who reported elevated levels of anxiety surrounding their vulnerability and concerns about securing needed care.

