Aim 1 will examine the impact of TEAM vs. TECH on the primary and secondary outcomes and will determine if changes in outcomes over time are different between the two groups. We will fit the GLMMs to associate each outcome with the intervention (TEAM vs. TECH) and other covariates of interest. To account for the within-patient correlation in longitudinal data and to reflect potential differences among three sites, we will add normally distributed random effects for patients and sites in addition to the fixed effects for intervention and covariates of interest. An inference of the intervention effects for each outcome will be carried out using Wald test based on the either F-distribution or Chi-square distribution as appropriate. For each outcome, the null hypothesis of homogeneous change in outcomes overtime between TEAM and TECH will be examined by testing the treatment-by-time interaction effect on each outcome. In the absence of significant interaction effects, the marginal difference in outcomes between TEAM and TECH will be examined using the same GLMMs without the interaction effect. All hypothesis tests for Aim 1 will be conducted at the overall significance level of 0.05. The score changes from baseline to each time point and their difference between TEAM and TECH will be estimated with 95% confidence intervals.

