
estimation of score changes in each outcome and their difference between TEAM and TECH will be presented with 95% confidence intervals for each subgroup of patients.

In handling missing data in quantitative analyses, we will attempt to determine the reasons for missing data and dropouts. The MAR assumption will be examined by comparing baseline characteristics between participants with and without missing data and conducting sensitivity analysis by repeating the main analyses without participants with missing data. If we observe statistical evidence that data are not MAR, we will stratify the participants into subgroups that share the same missing data pattern and estimate the statistical model separately for each missing data pattern. The results of all missing data analyses will be presented, and the sensitivity of our inference to the assumptions and approaches will be included in the interpretation of results.

COVID Considerations for Aims 1-2: Of our 675 projected participants, 32 were enrolled and completed their 6-month/primary outcomes surveys before the beginning of the COVID-19 (i.e., prior to March 12, 2020); 211 are potentially COVID-confounded (i.e., enrolled prior to or during the acute phase of the pandemic and were followed during it), and 432 were enrolled in the post-COVID phase of the study (after June 2021). Primary analyses will focus on the full sample of N=675, controlling for whether the participant was COVID-confounded. In sensitivity analyses, we will include only participants enrolled during the post-COVID phase. Effect sizes from sensitivity analyses will be assessed to evaluate whether findings are similar to those from the primary analyses.

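### The primary COVID adjustment is a single participant-level indicator with no stated time interaction, so it does not act on change from baseline, and by the stated counts it leaves 32 participants unflagged at a 12-month visit that falls in the pandemic

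*Combined protocol and SAP*

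**What the plan says.** The COVID paragraph at the end of the Quantitative Analysis section sorts the projected sample into three groups:

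- Before the pandemic: "32 were enrolled and completed their 6-month/primary outcomes surveys before the beginning of the COVID-19 (i.e., prior to March 12, 2020".
- Confounded: "211 are potentially COVID-confounded (i.e., enrolled prior to or during the acute phase of the pandemic and were followed during it".
- After: "432 were enrolled in the post-COVID phase of the study (after June 2021".

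The primary rule is then "Primary analyses will focus on the full sample of N=675, controlling for whether the participant was COVID-confounded". The paragraph does not say whether the indicator interacts with time or arm, and it defines no exposure by visit date. A sensitivity analysis restricted to the post-COVID enrollees follows, with effect sizes to be compared with the primary ones.

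For Aim 1, the same section tests treatment-by-time in a mixed model with patient and site random effects, and adds: "The score changes from baseline to each time point and their difference between TEAM and TECH will be estimated with 95% confidence intervals". Hypothesis 1 predicts clinically meaningful improvement in each arm. The Background and Significance section says: "Beginning in 2020, BH symptoms were further exacerbated by the COVID-19 pandemic". The Research Synopsis gives the accrual window: "Participants were actively enrolled in the study between July 1, 2019 and February 28, 2024".

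**The concern.** By the plan's own account the pandemic worsened behavioral health symptoms from 2020 on, so it acts on scores according to when they were measured. The stated control is instead a property of the person. Three things follow.

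1. A term that is constant within a person shifts baseline, 6-month and 12-month scores alike, so it drops out of the change between them.
2. The flagged group mixes people with a pre-pandemic baseline and pandemic follow-up with people whose baseline itself fell in the pandemic. These two patterns push change from baseline in opposite directions.
3. The early group is defined by the 6-month survey, but follow-up runs to 12 months.

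At stake is within-arm change. There is no untreated arm, so the improvement claimed under Hypothesis 1 is read directly from change from baseline, and randomisation does not protect that quantity.

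**Working it through.** **Reproducing the plan's split.** 32 + 211 + 432 = 675, as stated. The groups are therefore mutually exclusive, and the 32 are not among the 211. If the indicator marks the 211, the 32 are coded together with the 432 and make up 32/464 = 6.9% of the unflagged group.

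**Dates for the 32.** Enrollment opened July 1, 2019, so the earliest nominal 12-month visit is July 1, 2020, which is 111 days after March 12, 2020. All 32 are unexposed at baseline and 6 months, and all are exposed at 12 months.

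**Cancellation.** Write the mean score of person i at visit t as a + b·flag(i) + g(t) + d(t)·arm(i). The change from baseline is [g(t) - g(0)] + [d(t) - d(0)]·arm(i). The term b·flag(i) is gone from both the change and the treatment-by-time term.

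This was checked by simulation: 12 runs, N = 675 split 32/211/432, visits at 0, 6 and 12 months, random patient intercept. Assumed, not in the documents: total SD about 1; true change -0.4; pandemic shift in the flagged group of +0.2 at baseline and +0.5 afterwards; +0.5 at 12 months for the 32; more dropout among the flagged. The largest movement in any run on adding the flag as a main effect was:

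| | Change, 6 months | Change, 12 months | Treatment-by-time |
|---|---|---|---|
| Complete data | 0 (rounding error) | 0 (rounding error) | 0 (rounding error) |
| 25% dropout | 0.010 SD | 0.016 SD | 0.007 SD |

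**Size of the within-arm bias.** With complete data, bias at visit t = D × (number exposed at t - number exposed at baseline)/675. I assume D = 0.3 SD and an exposure window of March 12, 2020 to June 30, 2021 (476 days). Let k of the 211 have enrolled before the pandemic, and let the other 211 - k have enrolled evenly across the window.

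- The k early enrollees are unexposed at baseline and exposed at 6 and 12 months.
- Window enrollees are all exposed at baseline. At 6 months those enrolled before 2021 are still exposed (295/476 = 0.62). At 12 months those enrolled before July 2020 are (111/476 = 0.23).
- The 32 add exposure at 12 months only. The 432 are never exposed.

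So:

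- 6 months: 0.3 × [k - 0.38(211 - k)]/675
- 12 months: 0.3 × [32 + k - 0.77(211 - k)]/675

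| k | 6 months | 12 months |
|---|---|---|
| 0 | -0.036 SD | -0.058 SD |
| 60 | +0.001 SD | -0.011 SD |
| 80 | +0.013 SD | +0.005 SD |
| 120 | +0.038 SD | +0.037 SD |
| 211 | +0.094 SD | +0.108 SD |

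**Which k is plausible.** A nominal 6-month survey before March 12, 2020 means enrollment by about September 12, 2019. Thirty-two people in those 73 days is about 13 a month; the whole-trial rate is about 12 a month. Six more months to March 2020 at 13 a month gives roughly 80. Placing all 211 in those six months would need about 35 a month.

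**Share due to the 32.** 0.3 × 32/675 = 0.014 SD, at 12 months only.

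**The case against.** The strongest reply is that the plan already contains a clean estimate. The sensitivity analysis of the 432 post-COVID enrollees excludes both the 32 and the 211, so it is free of all three defects. That stands. But it drops 243 of 675 participants (36%), it is not the primary analysis, no criterion for similar findings is given, and it does not repair the estimate reported as primary.

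Second, the text says only that the analysis controls for the indicator. An interaction with time is unstated, not ruled out. The exact cancellation needs a main effect, an identity link and complete data, whereas the plan expects attrition and allows transformed outcomes. The main-effect flag also does some work in the fallback comparison of overall arm means when treatment-by-time is not significant. These points limit the claim to near-cancellation for the change and interaction results. They are also reasons to write down the form of the term.

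Third, the 32 are correctly unexposed at 6 months, the visit that the COVID paragraph ties to the primary outcomes. That stands too: their coding matters at 12 months only, and it is inferred from the counts.

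A reader might infer that the TEAM-TECH comparison is compromised. The documents do not support that. Randomisation in blocks of two and four keeps the arms close to balanced over calendar time, and in the simulation the treatment-by-time terms moved on average by about 0.006 SD or less under any version of the COVID term. The contrast would be at risk only if the pandemic changed the arms' relative effect.

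A reader might also take 0.11 SD as the expected bias. That figure requires all 211 to have enrolled before the pandemic. The plan says before or during it, and the accrual rate points to a far smaller value.

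**Conclusion.** The point holds at modest size. As written, the primary COVID control does not act on change from baseline or on the treatment-by-time test, apart from shifts of about 0.01 to 0.02 SD in the changes under 25% dropout in the simulation above. Calling those results COVID-adjusted would mislead. By the stated counts the indicator is also wrong at 12 months for the 32, who meet the plan's own description of the confounded group by then.

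The consequence is for within-arm change under Hypothesis 1. The likely bias is about 0.01 SD, and the range over all splits is about -0.06 to +0.11 SD, against pilot within-arm effects of 0.16 to 0.49 in the power section. These sizes rest on the assumed 0.3 SD pandemic effect, even accrual within periods, nominal visit dates and complete data. The cancellation does not depend on the 0.3 SD or on the accrual pattern.

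**What to change.** In the primary Aim 1 and Aim 2 models, replace the participant flag with a time-varying indicator set by the date of each assessment, baseline included: before March 12, 2020; March 12, 2020 to June 30, 2021; after June 2021. Report within-arm changes standardised to one stated period. Count the 32 as exposed at 12 months only. Keep the post-COVID-only sensitivity analysis.

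The cost is one variable recoded from assessment dates, revised SAP wording and two degrees of freedom. The added assumption is that the pandemic effect is constant within each period. Recoding does not turn uncontrolled within-arm change into a causal effect; it removes one known distortion from it.

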#### **Qualitative Analysis**

For Aim 3, qualitative interviews will be transcribed verbatim to support the analytic process. Separate codebooks for patients and provider interviews will be constructed and follow standard editing methods, including audit trails to document creation of codes during the iterative process. Two trained independent analysts will code the interviews in Dedoose, an qualitative analysis software. After each transcript is coded, coders will meet to process and adjudicate differences until agreement is achieved. Codes determined through this process will be recorded in a master file to be used in final analysis. For each qualitative cohort and wave of data, we will examine key topics to better understand barriers and facilitators to intervention implementation and how SMHs impact patients' ability to manage IBD and behavioral health conditions. In addition, for each subsequent wave of data collection, we will examine changes and consistency across the data waves.

#### **Informed Consent Process**

If a patient is eligible and is interested in participating in the study, the research assistants/research staff will provide the patient with a copy of the consent form to review and obtain informed consent during a clinic visit. Patients will be given the opportunity to take the consent form home to further consider participation in the study. Participants may return the signed consent form by using a prepaid envelope provided by the study team or in-person at later clinic visit.

Study participants will be given a copy of the informed consent to read and research staff will be available to describe its content and answer any questions about the study. Any questions that cannot be answered by research staff will be referred to the PI prior to proceeding with the consent process. All participants will be given an opportunity to take the informed consent document home for further consideration before consenting. Research staff will provide participants with contact information for research staff and the PI so that any questions they may have can be answered before providing consent. Research staff will make it clear to participants that their decision to participate or not in the study will have no impact on the medical care they receive and will stress to the participant that participation in the study is voluntary (their choice). Research staff will also make it clear to participants that they may withdraw their consent at any time during the course of the study.

## **Privacy and Confidentiality**

Self-report and qualitative data collected for this study will be used for research purposes only. Access to the data will be restricted to the PI, Co-Is, and other Research Team members trained in UPMC and University of Pittsburgh HRPO Human Subject Research Training requirements. Research staff will sign confidentiality agreements as required. Identifying links to all data will be maintained at baseline and other data collection time points using a secure password-protected server, accessible only by authorized members of the study team. Once the data is collected, the file containing the link between identifying information and the participant's data will be destroyed.

Qualitative data will be audio recorded using digital recording devices, transferred to a secure server immediately following recording and deleted as soon as it is fully transcribed. Interviews will be audio recorded, transcribed, and scrubbed of identifying information. Participants will be asked not to include any identifying information in their responses, and coders will not code any identifying information that may be provided inadvertently.

All data obtained over the course of the study will be confidential and secure. Paper study records will be secured using the "double-lock" method (i.e., in a locked cabinet within a locked office). Data stored on computers will be password protected and stored on a secure server behind the organization's firewall. Each Research Team member has a unique network account and a secure password that complies with existing institutional policies and procedures. Only members of the team who are authorized by the PI will have access to the secured files. Identities of participants will not be revealed in the publication or presentation of any results from this study.

## Risk/Benefit

#### **Risk to Participants**

## Infrequent (Rare) Risks:

- The risks associated with this study include the potential for a breach of confidentiality for both groups in the study. To reduce the risk of that happening, we will protect the confidentiality of this information by giving all participants a unique study ID that will be kept separate from any identifying information. The final data set will be de-identified prior to analysis and done so according to HIPAA standards.

- Participants will be asked questions about private, personal matters and information related to their health. They may feel uncomfortable answering questionnaires or assessments or discussing their health with the research team. They may also feel tired from answering questionnaires or having discussions with the research team. There are no known psychological or physical risks associated with the questionnaires and assessments that will be used for this study. Participants will be given the option to stop the assessments or take a break at any time.
- Participants will be monitored by the PI and other members of the research team throughout the duration of the research study. If a participant reports clinical distress to a member of the research team (via study assessment or other form of communication), then the research team will immediately contact the PI. The PI will contact the participant personally to ensure their immediate safety and offer referral for appropriate care. If a clinically significant, unexpected disease or condition is identified during the conduct of the study, members of the IBD SMH will systematically monitor the physical health status of all participating patients through routine care management and patient-level interactions. The assessment of adverse medical sequelae will be managed through a participant's existing and routine care. If during research assessments a high level of medical risk is identified, the research team will attempt to ascertain the nature and level of risk and immediately contact IBD SMH clinical staff for direct follow-up with the participant. The IBD SMH clinical staff will directly contact the participant and refer them to the appropriate level of care in accordance with established protocols
- Electronic or smartphone communications (e.g., text messages, emails, video visits) or internet communication that may happen as part of normal IBD care cannot be guaranteed as confidential. It is possible that confidential information may be collected and used by individuals who do not have permission to do so. All study sites take precautions to prevent this from happening, but there is still a risk that confidentiality may be breached. All electronic study records will be password protected and stored on secure institutional networks or REDCap Cloud, a HIPAA-compliant and secure webbased data collection platform. Paper-based records will be stored in locked filing cabinets and only accessible to members of the research team.

